### 16.3. Appendix 3: Assessment Windows

#### 16.3.1. Definition of Weekly Assessment Windows

Daily assessments of BFI item 3 and HES daily symptoms as well as weekly assessments of the full BFI will be assigned a single weekly analysis time point according to the table below.

Analysis Timepoint	Analysis Window		
	Beginning Timepoint	Ending Timepoint	Special Rules for Handling Overlapping Timepoints
Week 32	Week 32 (Visit 11) visit date – 6 days	Week 32 (Visit 11) visit date	
Week 31	Week 32 (Visit 11) visit date – 13 days	Week 32 (Visit 11) visit date – 7 days	If assessment falls into Week 31/Week 30/Week 29 and Week 28, assign assessment as Week 28. If assessment date is less than Week 28 (Visit 10) visit date, assign a relevant timepoint less than Week 28.
Week 30	Week 32 (Visit 11) visit date – 20 days	Week 32 (Visit 11) visit date – 14 days	
Week 29	Week 32 (Visit 11) visit date – 27 days	Week 32 (Visit 11) visit date – 21 days	
Week 28	Week 28 (Visit 10) visit date – 6 days	Week 28 (Visit 10) visit date	
Week 27	Week 28 (Visit 10) visit date – 13 days	Week 28 (Visit 10) visit date – 7 days	If assessment falls into Week 27/Week 26/Week 25 and Week 24, assign assessment as Week 24.
Week 26	Week 28 (Visit 10) visit date – 20 days	Week 28 (Visit 10) visit date – 14 days	
Week 25	Week 28 (Visit 10) visit date – 27 days	Week 28 (Visit 10) visit date – 21 days	If assessment date is less than Week 24 (Visit 9) visit date, assign a relevant timepoint less than Week 24.
Week 24	Week 24 (Visit 9) visit date – 6 days	Week 24 (Visit 9) visit date	
Week 23	Week 24 (Visit 9) visit date – 13 days	Week 24 (Visit 9) visit date – 7 days	If assessment falls into Week 23/Week 22/Week 21 and Week 20, assign assessment as Week 20.
Week 22	Week 24 (Visit 9) visit date – 20 days	Week 24 (Visit 9) visit date – 14 days	
Week 21	Week 24 (Visit 9) visit date – 27 days	Week 24 (Visit 9) visit date – 21 days	If assessment date is less than Week 20 (Visit 8) visit date, assign a relevant timepoint less than Week 20.
Week 20	Week 20 (Visit 8) visit date – 6 days	Week 20 (Visit 8) visit date	
Week 19	Week 20 (Visit 8) visit date – 13 days	Week 20 (Visit 8) visit date – 7 days	If assessment falls into Week 19/Week 18/Week 17 and Week 16, assign assessment as Week 16.
Week 18	Week 20 (Visit 8) visit date – 20 days	Week 20 (Visit 8) visit date – 14 days	
Week 17	Week 20 (Visit 8) visit date – 27 days	Week 20 (Visit 8) visit date – 21 days	If assessment date is less than Week 16 (Visit 7) visit date, assign a relevant timepoint less than

Analysis Timepoint	Analysis Window		
	Beginning Timepoint	Ending Timepoint	Special Rules for Handling Overlapping Timepoints
			Week 16.
Week 16	Week 16 (Visit 7) visit date – 6 days	Week 16 (Visit 7) visit date	
Week 15	Week 16 (Visit 7) visit date – 13 days	Week 16 (Visit 7) visit date – 7 days	If assessment falls into Week 15/Week 14/Week 13 and Week 12, assign assessment as Week 12.
Week 14	Week 16 (Visit 7) visit date – 20 days	Week 16 (Visit 7) visit date – 14 days	
Week 13	Week 16 (Visit 7) visit date – 27 days	Week 16 (Visit 7) visit date – 21 days	
Week 12	Week 12 (Visit 6) visit date – 6 days	Week 12 (Visit 6) visit date	
Week 11	Week 12 (Visit 6) visit date – 13 days	Week 12 (Visit 6) visit date – 7 days	If assessment falls into Week 11/Week 10/Week 9 and Week 8, assign assessment as Week 8. If assessment date is less than Week 8 (Visit 5) visit date, assign a relevant timepoint less than Week 8.
Week 10	Week 12 (Visit 6) visit date – 20 days	Week 12 (Visit 6) visit date – 14 days	
Week 9	Week 12 (Visit 6) visit date – 27 days	Week 12 (Visit 6) visit date – 21 days	
Week 8	Week 8 (Visit 5) visit date – 6 days	Week 8 (Visit 5) visit date	
Week 7	Week 8 (Visit 5) visit date – 13 days	Week 8 (Visit 5) visit date – 7 days	If assessment falls into Week 7/Week 6/Week 5 and Week 4, assign assessment as Week 4. If assessment date is less than Week 4 (Visit 4) visit date, assign a relevant timepoint less than Week 4.
Week 6	Week 8 (Visit 5) visit date – 20 days	Week 8 (Visit 5) visit date – 14 days	
Week 5	Week 8 (Visit 5) visit date – 27 days	Week 8 (Visit 5) visit date – 21 days	
Week 4	Week 4 (Visit 4) visit date – 6 days	Week 4 (Visit 4) visit date	
Week 3	Week 4 (Visit 4) visit date – 13 days	Week 4 (Visit 4) visit date – 7 days	If assessment falls into Week 3/Week 2/Week 1 and Baseline (Week 0) or Screening, assign assessment as Baseline (Week 0) or Screening.
Week 2	Week 4 (Visit 4) visit date – 20 days	Week 4 (Visit 4) visit date – 14 days	
Week 1	Week 4 (Visit 4) visit date – 27 days	Week 4 (Visit 4) visit date – 21 days	
Baseline (Week 0)	Date of first dose of study treatment – 7 days	Date of first dose of study treatment - 1	
Screening	N/A	Date of first dose of study treatment – 8 days	

## 16.4. Appendix 4: Study Phases

Assessments and events will be classified according to the time of occurrence relative to the first dose of study treatment.

### 16.4.1. Treatment Phases for HES Flare

Study Phase	Definition
Pre-Treatment	Flare onset date < Date of first dose of study treatment
On-Treatment	Date of first dose of study treatment ≤ Flare onset date ≤ Date of last dose of study treatment + 28 days
Off-Treatment	Date of last dose of study treatment + 28 days < Flare onset date ≤ Date of Week 32 visit /Study withdrawal date
Post-Treatment	Flare onset date > Date of Week 32 visit

### 16.4.2. Treatment Phases for BFI and HES-DS

Since the electronic diary is completed daily in the evening, BFI and HES-DS assessments will be classified as follows:

Study Phase	Definition
Pre-Treatment	Assessment date < Date of first dose of study treatment
On-Treatment	Date of first dose of study treatment ≤ Assessment date ≤ Date of last dose of study treatment + 28 days
Off-Treatment	Date of last dose of study treatment + 28 days < Assessment date ≤ Date of Week 32 visit /Study withdrawal date
Post-Treatment	Assessment date > Date of Week 32 visit

### 16.4.3. Treatment Phases for Other Efficacy Assessments

Study Phase	Definition
Pre-Treatment	Assessment date ≤ Date of first dose of study treatment
On-Treatment	Date of first dose of study treatment < Assessment date ≤ Date of last dose of study treatment + 28 days
Off-Treatment	Date of last dose of study treatment + 28 days < Assessment date ≤ Date of Week 32 visit /Study withdrawal date
Post-Treatment	Assessment date > Date of Week 32 visit

### 16.4.4. Treatment Phases for Adverse Events

Study Phase	Definition
Pre-Treatment	AE onset date/time < Date/time of first dose of study treatment
On-Treatment	Date/time of first dose of study treatment ≤ AE onset date/time ≤ Date of last dose of study treatment + 28 days
Post-Treatment	AE onset date > Date of last dose of study treatment + 28 days

#### NOTES:

- Please refer to Section 16.7.2.1 for handling of missing and partial dates for adverse events.

**16.4.5. Study Phases for Concomitant Medication**

Study Phase	Definition
Prior	If medication end date is not missing and is before the date of first dose of study treatment
Concomitant	Any medication that is not a prior

**NOTES:**

- Please refer to Section [16.7.2.1](#) for handling of missing and partial dates for concomitant medications.

## 16.5. Appendix 5: Data Display Standards & Handling Conventions

### 16.5.1. Reporting Process

Software	

 
The currently supported version of SAS software (SAS 9.4 or later) will be used.
 
	
Reporting Area	
HARP Server	: uk1salx00175
HARP Area	: sb240563/mid200622
Analysis Datasets	

 
Analysis datasets will be created according to CDISC standards.
 
For creation of ADaM datasets (ADCM/ADAE), the same version of dictionary datasets will be implemented for conversion from SI to SDTM.
 
	
Generation of RTF Files	

 
RTF files will be generated for the final reporting effort.
 
	

### 16.5.2. Reporting Standards

General

 
All data displays (Tables, Figures & Listings) will use the term “Subject” rather than “Participant” which reflects CDISC and GSK Data Display Standards terminology.
 
The current GSK Integrated Data Standards Library (IDSL) will be applied for reporting, unless otherwise stated (IDSL Standards Location: https://spope.gsk.com/sites/IDSLLibrary/SitePages/Home.aspx): 
 
4.03 to 4.23: General Principles
 
5.01 to 5.08: Principles Related to Data Listings
 
6.01 to 6.11: Principles Related to Summary Tables
 
7.01 to 7.13: Principles Related to Graphics
 
 
 
Do not include subject level listings in the main body of the GSK Clinical Study Report. All subject level listings should be located in the modular appendices as ICH or non-ICH listings
 

Formats

 
GSK IDSL Statistical Principles (5.03 & 6.06.3) for decimal places (DPs) will be adopted for reporting of data based on the raw data collected but may be adjusted to a clinically interpretable number of DPs.
 
For FEV1 and FVC, the mean and median (L) will be reported to 3 decimal places (i.e. to the nearest mL), SD to 4 decimal places, minimum and maximum to 2 decimal places.
 

Planned and Actual Time

 
Reporting for tables, figures and formal statistical analyses: 
 
Planned time relative to dosing will be used in figures, summaries, statistical analyses and calculation of any derived parameters, unless otherwise stated.
 
The impact of any major deviation from the planned assessment times and/or scheduled visit days on the analyses and interpretation of the results will be assessed as appropriate.
 
 
 


 
Reporting for Data Listings:             
 
Planned and actual time relative to study drug dosing will be shown in listings (Refer to IDSL Statistical Principle 5.05.1).
 
Unscheduled or unplanned readings will be presented within the subject's listings.
 
 
 
Visits outside the protocol defined time-windows (i.e. recorded as protocol deviations) will be included in listings, summaries and statistical analyses.
 
	
Unscheduled Visits	

 
HES flare data collected at unscheduled visits will be included in the derivation of all flare related endpoints for summary and analysis.
 
For summaries by visit, data recorded at an unscheduled visit will be re-assigned in the ADaM data sets to the closest nominal visit at which collection of data was scheduled, unless information already exists at that visit. Unscheduled data re-assigned to a scheduled visit will be included in analyses, summary tables and figures by scheduled visit. Unscheduled data that is not re-assigned to a scheduled visit will not be included in analyses, summary tables or figures by scheduled visit. Unscheduled data that is not re-assigned to a scheduled visit will be considered in the derivation of baseline and highest/worst case post baseline result for relevant summary tables.
 
Data recorded at unscheduled visits will be included in the assessment of maximum or worst case post-baseline for relevant endpoints.
 
All unscheduled visits will be included in listings.
 
	
Early Withdrawal Visits	

 
Data recorded at the early withdrawal visit will be re-assigned in the ADaM data sets to the next scheduled visit, unless information already exists at that visit. Early withdrawal data re-assigned to a scheduled visit will be included in analyses, summary tables and figures by scheduled visit. Early withdrawal visit data that is not re-assigned to a scheduled visit will not be included in analyses, summary tables or figures by scheduled visit.
 
Data recorded at early withdrawal visits will be included in the assessment of maximum or worst case post-baseline for relevant endpoints.
 
Data from all early withdrawal visits will be included in listings.
 
	
Descriptive Summary Statistics	
Continuous Data	Refer to IDSL Statistical Principle 6.06.1
Categorical Data	N, n, frequency, %
Graphical Displays	

 
Refer to IDSL Statistical Principals 7.01 to 7.13.
 
	

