9. Refer to Section 6.4 for additional blood draw between the scheduled clinical visits for subjects who will administer blinded OCS.
10. Clinical chemistry will include analytes and liver chemistry monitoring.
11. Negative urine pregnancy test result must be confirmed prior to dosing in women of reproductive potential.
12. Lipoprotein (fasting) included in clinical chemistry. Subject must be in a fasting state. If the subject has not fasted, he/she may return to the clinic to collect this sample.
13. Urine tests are done using dipstick. If found abnormal, the urine sample will be sent to the central laboratory for further testing.
14. If test was performed within 3 months prior to randomization, testing at screening is not required.
15. F/P test is required if no documented results are available.
16. Informed consent for optional sub-studies (e.g., genetics research) must be obtained before collecting a sample. Genetic sample collection is recommended at Visit 2, but may be drawn at any time after the subject is consented and randomized.
17. Sample collection for the optional biomarker sub-study should be done after obtaining a written consent.
18. The date and time of the administration of study treatment will be recorded in the CRF. For safety monitoring requirement, refer to Section 6.2.
19. Assessments will be collected when possible depending on the clinical status during worsening of symptoms between scheduled clinic visits to evaluate for an HES flare. Spirometry for a respiratory flare, and troponin, echocardiogram, & ECG for a CV flare will be performed (Selective assessments depending on the type of flare are noted in the table with the gray shade). Echocardiogram will be performed only if there is a change in HF classification (see Section 12.7) and/or the investigator determines that there is a need for assessment. When attending the clinic visit at the time of a suspected HES flare is not possible, the investigator should make every effort to evaluate the subject via telephone and complete the HES Core Assessments (Section 7.3.2).
20. Subjects who prematurely discontinue study treatment will continue to attend 4-weekly scheduled clinic visit and complete these assessments. Blood samples for hematology will be collected at these visits for blinded blood eosinophil monitoring (Section 6.4). All other laboratory assessments are completed at 4 and 12 weeks after the last dose only as noted in footnote #21.

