7.12.7. SF-36 V2

The SF-36 v2 is a health status survey with 36 questions [Maruish, 2011]. It yields an 8-scale profile of functional health and well-being scores as well as psychometrically-based

physical and mental health summary measures and a preference-based health utility index. It is a generic measure, as opposed to one that targets a specific age, disease, or treatment group. Accordingly, the SF-36 v2 has proven useful in differentiating the health benefits produced by a wide range of different treatments.

The SF-36 v2 assesses eight health concepts: 1) limitations in physical activities because of health problems; 2) limitations in social activities because of physical or emotional problems; 3) limitations in usual role activities because of physical health problems; 4) bodily pain; 5) general mental health (psychological distress and well-being); 6) limitations in usual role activities because of emotional problems; 7) vitality (energy and fatigue); and 8) general health perceptions. The survey was constructed for self-administration by persons 14 years of age and older.

The SF-36 will be completed with a 4-week recall at a scheduled clinic visits as specified in Section 7.1, to support assessment of overall change in health-related quality of life (HRQoL). The SF-36 will be completed with a 1-week recall at an unscheduled 'Flare' visit, to provide an assessment of the impact of flare on HRQoL.

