#### 7.6.7.1. Endpoint / Variables

At each visit, subjects are asked to rate their symptoms of HES now as none (0), mild (1), moderate (2), severe (3) or very severe (4). The change from baseline at Week 32 will be calculated from the Week 32 assessment and the Week 0 assessment and expressed in terms of number of categories of improvement or worsening of symptoms i.e. 4 point improvement (-4), 3 point improvement (-3), 2 point improvement (-2), 1 point improvement (-1), no change (0), 1 point worsening (1), 2 point worsening (2), 3 point worsening (3) or 4 point worsening (4).

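### SAP 16.5.2 lets Flare-visit SF-36 forms (1-week recall) and flare-prompted spirometry fill an empty scheduled visit: a minor defect with a one-sentence correction

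*SAP*

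**What the plan says.** **Re-assignment rule.** Under SAP 16.5.2 (Unscheduled Visits), results from "an unscheduled visit will be re-assigned in the ADaM data sets to the closest nominal visit at which collection of data was scheduled". This applies only if the target visit is empty. The SAP's next sentence reads: "Unscheduled data re-assigned to a scheduled visit will be included in analyses, summary tables and figures by scheduled visit". No window is given. The February 2019 SAP carries the same rule in its section 15.5.2.

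**Flare endpoints.** The same block says: "HES flare data collected at unscheduled visits will be included in the derivation of all flare related endpoints". This governs flare events and does not exempt other measurements taken at those visits.

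**The Flare visit.** Protocol 4.2, 7.3.1 and 7.12.7 describe it as unscheduled. It takes place when the investigator suspects a flare between clinic visits.

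**SF-36.** Protocol 7.12.7 says: "The SF-36 will be completed with a 4-week recall at a scheduled clinic visits", to assess overall change in quality of life. It also says: "The SF-36 will be completed with a 1-week recall at an unscheduled" Flare visit, to assess the impact of the flare. SAP 8.1 summarises the scores by visit (Tables 3.1 and 3.2), does not mention recall, and plans no statistical analysis.

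**Spirometry.** Protocol 7.1, footnote 19, says: "Spirometry for a respiratory flare, and troponin, echocardiogram, & ECG for a CV flare will be performed". SAP 7.6.2 analyses FEV1 and FVC by visit in a mixed model that assumes missing data are missing at random (MAR).

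**The concern.** The protocol keeps the two SF-36 forms apart by recall period and by purpose. The SAP rule can put both in one table column under one visit label, with nothing to tell the reader.

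Spirometry raises a different issue. A Flare-visit reading exists because the patient was thought to be worsening. When it fills an empty Week 8, 16, 24 or 32 cell, the model treats it as the value that would have been measured at that visit. The MAR assumption covers values that are absent. It does not justify inserting a value whose timing was chosen by worsening. If such visits are more common on placebo, the insertion would tend to make placebo lung function look worse.

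At stake is the labelling of one descriptive outcome and the cleanness of one exploratory model.

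**Working it through.** The plan gives no figure on this point to reproduce. The check is a reading of the text followed by a calculation of scale.

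**1. Does the rule reach Flare visits?** SAP 16.5.2 covers any unscheduled visit, the protocol calls the Flare visit unscheduled, and SAP 7.6.2 and 8.1 contain no exception. As written, it does. Data go only to the single closest scheduled visit. If that visit already holds a value, they are not moved elsewhere.

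**2. How far can a value travel?** The rule has no limit, but the schedule in Protocol 7.1 implies one between visits: half the gap between scheduled assessments.
- SF-36, every 4 weeks: 4/2 = 2 weeks.
- Spirometry, Weeks 0, 8, 16, 24 and 32: 8/2 = 4 weeks.

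**3. Which visits can be empty?** Missed visits are one source. Early stopping of study treatment is another. Those subjects stay in the study to Week 32, but as extracted, their column in the Protocol 7.1 table has no entry for SF-36 or spirometry. Their scheduled visits may then be empty by design. Check this against the original table: column alignment is uncertain in the extracted text, and the SAP's copy of the SF-36 row shows an extra mark. The SAP also does not say whether a visit counts as scheduled for the study or for the individual subject.

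**4. Scale.** Inputs from Protocol 9.2.1: 40 per arm, with flare proportions of 60% (placebo) and 22% (mepolizumab). Assumptions without a source in the documents: one flare per flaring subject, uniform over 32 weeks, a Flare visit each time, emptiness independent of flare, and a proportion q = 5-20% of scheduled values empty.

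Expected moved values = 40 x flare proportion x share of flare times closest to the visit x q.

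| Measure | Time share | Placebo | Mepolizumab |
|---|---|---|---|
| SF-36, Week 32 | 2/32 | 1.5q = 0.08-0.30 | 0.55q = 0.03-0.11 |
| Spirometry, Week 32 | 4/32 | 3.0q = 0.15-0.60 | 1.1q = 0.06-0.22 |
| SF-36, all post-baseline visits | 30/32 | 22.5q = 1.1-4.5 | 8.25q = 0.4-1.7 |
| Spirometry, all post-baseline visits | 28/32 | 21q = 1.1-4.2 | 7.7q = 0.4-1.5 |

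The spirometry rows treat every flare as respiratory, so they are high. Protocol 2.2 cites 25% pulmonary manifestations in one retrospective series. Used as an illustrative share, it gives 0.04-0.15 and 0.01-0.06 at Week 32.

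**5. Effect on FEV1.** Take an assumed drop of 200-400 mL during a flare (no source in the documents).
- Week 32: the difference between arms in the share of flare values is (0.60 - 0.22) x 4/32 x q = 0.0475q = 0.24-0.95 percentage points. Multiplied by 200-400 mL, this is about 0.5-3.8 mL if all flares are respiratory, or 0.1-1.0 mL at a 25% share.
- Weeks 8, 16 and 24: the time share is 8/32, so the figures double to about 1.0-7.6 mL, or 0.2-1.9 mL at a 25% share.

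All results are proportional to q, so a reader with another view of missingness can rescale them.

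**The case against.** The strongest reply is that this is a pre-specified convention, blind to arm, that keeps observed data, and that little hangs on it. Much of that stands.

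- **Endpoints.** The primary endpoint and the flare-based secondaries rest on flare events. BFI item 3 and HES-DS have their own date windows in SAP 16.3.1. SF-36 has no inferential analysis, and FEV1 and FVC are exploratory.
- **Existing safeguards.** SAP 16.5.2 promises to assess the impact of major departures from planned assessment times as appropriate, and lists all unscheduled visits. This helps, but it is not a rule and does not address recall.
- **Real effect.** Under the treatment policy strategy of SAP 7.6.2.2, worse lung function from more flares is partly a true treatment effect. Any gap in FEV1 cannot all be called false.

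Three stronger readings are tempting, and the documents do not support them.

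- **Flare-visit values arise 2.7 times as often on placebo.** 60/22 = 2.7 is a ratio of flaring subjects. Flares under definition b) are triggered by blood counts. Others may be found at scheduled visits or assessed by telephone. Suspected flares that are not confirmed add Flare visits outside the 60% and 22%.
- **Gaps are filled only for patients who flared.** A Flare visit follows a suspected flare, and any other unscheduled visit can also fill a gap.
- **All Flare-visit patient-reported outcomes should be barred.** For SSR and MSAS-SF, SAP 7.6.7.2 and 7.6.8.2 give a subject missing Week 32 the worst value seen in any subject. Barring re-assignment would replace observed flare-time scores with that value, possibly more often on placebo. The present rule treats two subjects missing Week 32 differently, but the alternative is a trade-off and not a clear correction.

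**Conclusion.** The defect is real and minor. For SF-36 it follows from the text alone: any Flare-visit form that is moved has the wrong recall period for its column, in descriptive Tables 3.1 and 3.2 only. For spirometry, a reading prompted by suspected worsening can enter the MAR model as a routine value.

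Under the assumptions in the working, fewer than one value per arm would move at Week 32 for either measure, and a handful at most over the whole study. An FEV1 effect would be a few millilitres or less, and it rests on an assumed flare-time drop. If subjects who stop treatment early have no scheduled SF-36 or spirometry, more visits could be empty than 5-20%. That depends on the original schedule table and on how the SAP uses the word scheduled. Nothing here bears on the trial's main conclusions, and the documents do not establish a bias in favour of either arm.

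**What to change.** Add to SAP 16.5.2, before unblinding: SF-36 and spirometry collected at an unscheduled Flare visit are not re-assigned to a scheduled visit. They are listed and summarised separately as flare-visit data, and the scheduled visit stays missing. For FEV1 and FVC, the existing MAR handling then applies.

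Leave the SSR and MSAS-SF rule unchanged.

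The cost is one sentence, a filter in the analysis datasets and a small flare-visit summary. The downside is a few more missing by-visit values.
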